### 11.3 Pooling of Centers in Multi-Center Studies

As no site-level analyses are planned, there will be no pooling of centers.

### 11.4 Multiple Comparisons/Multiplicity

No adjustments for multiple comparisons or multiplicity will be made.

### 11.5 Examination of Subgroups

To evaluate the consistency of the results of the primary and secondary efficacy analysis across different subgroups of interest, the primary analysis specified above ([Section 9.1](#)) will be repeated, stratifying for each of the following subgroups specified below:

- Age (< 18 years, 18+ years)

Additionally, to evaluate the exploratory objectives of this study in patients of different age groups, body weight loss, change from baseline in BMI, weight, and waist circumference (described in [Sections 9.3.2](#) and [9.3.3](#)) will be stratified by:

- Age (6 - < 18 years, 18+ years)
- Pediatric age (6 - < 12 years, 12 - < 18 years)

## 12 Interim Analysis and Data Monitoring

There is no planned interim analysis for the purposes of modifying the study.

## 13 Quality Control

All data displays and analyses will adhere to the International Conference on Harmonization (ICH) *Harmonized Tripartite Guideline: Structure and Content of Clinical Study Reports (ICH Topic E3)*.

All analyses will be performed using SAS® Version 9.4 (or later). Advanced Clinical will follow its standard operating procedures in the creation and quality control of all tables, listings, figures, and analyses. Sponsor or its designee will review all tables, listings, and figures prior to final database lock. All final SAS programs and associated output files will be transferred to Sponsor in agreed-upon format at project completion.

## 14 Tables and Listings Conventions

Mock-ups for statistical tables and listings will be provided. Final formats for the statistical tables and listings may deviate from these mock-ups upon agreement with the Sponsor. Footnotes will be used as needed to clarify the information that is presented in the tables and listings. Unless otherwise requested by the Sponsor, the term ‘patient’ will be used in all tables and listings, in accordance with Clinical Data Interchange Standards Consortium (CDISC) standards.

The table and listing mock shells, along with their programming convention, will be provided in a separate document.

## 16 Appendices

### 16.1 Schedule of Assessments

Table 1: Schedule of Activities

Study Period/Procedure	Screening	Study Treatment						EOS Visit	Treatment Discontinuation Visit
		V1	V2	-	V3 	V4	V5	V6 	
Clinic Visit Number	V1	V2	-	V3 	V4	V5	V6 	V7 	
Study Day	-56 to -14	1	15	29	57	85	113	141	
Visit Window (days)	-	-	+3d	± 4 d	± 4 d	± 4 d	± 4 d	± 4 d	± 4 d
Informed consent/assent 	X								
Inclusion/exclusion criteria review	X	X							
Medical history review	X								
Physical examination 	X	X		X	X	X	X	X	X
Comprehensive skin examination 	X						X		X
Fitzpatrick classification scale	X						X	X	X
Weight 	X	X		X	X	X	X	X	X
Waist circumference 	X	X		X	X	X	X	X	X
Height 	X			X	X	X	X	X	X
Body composition assessment by DXA 	X						X		X
Vital signs 	X	X		X	X	X	X	X	X
ECG (12-lead) 	X	X 		X 			X 		X
Pregnancy test 	X	X 		X	X 	X 	X 		X
Daily hunger questionnaires 	X				Daily				X
Global hunger assessment 		X 		X 	X 	X 	X 	X	X
PHQ-A or PHQ-9 	X	X 		X 	X 	X 	X 	X	X
C-SSRS 	X	X 		X 	X 	X 	X 	X	X
SF-12 or SF-10 	X	X 		X 			X 		X
IWQOL-Lite-CT 	X	X 		X 			X 		X

Study Period/Procedure	Screening	Study Treatment						EOS Visit	Treatment Discontinuation Visit
		V1	V2	-	V3 	V4	V5	V6 	
Clinic Visit Number	V1	V2	-	V3 	V4	V5	V6 	V7 	
Study Day	-56 to -14	1	15	29	57	85	113	141	
Visit Window (days)	-	-	+3d	± 4 d	± 4 d	± 4 d	± 4 d	± 4 d	
EQ-5D-5L or Y 	X	X 		X 			X 		X
Safety laboratory tests 	X	X		X 	X 	X 	X 	X	X
FSH*	X								
Injection site inspection 			X		X	X	X		X
Telephone call 				X					
Review of type of lesion on MRI 	X								
Study drug administration 				Daily dosing					
Dispense/Return study drug 			X		X	X	X		
Adverse event assessment 	X	X	X	X	X	X	X	X	X
Concomitant medications review	X	X	X	X	X	X	X	X	X

D = Days; EOS = End of Study; PK = Pharmacokinetics; V = Study Visit Number.

1. Patients who are <16 years of age will receive first daily dose of 3.0 mg at V3, at the clinic.
2. Study endpoints are analyzed at V6. After completing V6. Patients meeting the primary endpoint may be eligible to be enrolled in a separate extension study, Rhythm Study RM-493-022, under which auspices the patient will continue to receive setmelanotide. Patients who do not meet the primary endpoint or elect not to continue setmelanotide are to discontinue setmelanotide at Visit 6 and return for an End-of-Study Visit (Visit 7) 4 weeks thereafter for a final safety review under the auspices of the current study.
3. Although the study procedures and assessments required per protocol are classified as "No or Minimal Risk" (with the exception of DXA which may be classified as "Minor Increase over Minimal Risk") according to the 2008 Guidance Document "Ethical Considerations for Clinical Trials on Medicinal Products Conducted with the Pediatric Population," considerations for reducing pain in distress in patients younger than 18 years of age are included in [Appendix 2](#).
4. A complete physical examination will be conducted at Screening and at the EOS V7. At other time points, an abbreviated examination will be performed. The abbreviated examination should focus on heart, lungs, skin, neurologic exam, and any areas of previous abnormal findings, noting any changes from baseline. In addition, Tanner Staging for assessment of pubertal development will be conducted for those patients who have yet to reach Tanner Stage V. Whenever possible, the same trained health care professional will conduct the exam and Tanner Staging.
5. A comprehensive skin examination will be performed by the Investigator. The skin examination should include a full body (head-to-toe skin examination). If any concerning lesions are identified during Screening, the patient should be referred to a dermatologist. Any concerning lesions will be biopsied by the dermatologist and results must be benign prior to the first dose of setmelanotide. If the pre-treatment biopsy results are of concern, the patient will be excluded from the study. Additionally, any concerning lesion or change in an existing lesion during the course of the study must be evaluated by the dermatologist and biopsied, if clinically indicated in the opinion of the dermatologist.
6. Weight (kg) is to be measured at the clinic using the same scale throughout the study, including the Screening Visit, after patients have emptied their bladders and pockets and after fasting for at least 8 hours. Patients are to wear light clothing or underwear and no shoes, and will be weighed at approximately the same time of day. Weight should be recorded to the nearest 10th of a decimal place if reported by a digital scale or to the nearest half of a Kg if reported by a mechanical scale.
7. Waist circumference (cm) will be done in triplicate and recorded to the nearest half cm. Waist circumference should be measured after patients have fasted for at least 8 hours and at approximately the same time at each visit. Patients should be standing and in light clothing and have emptied their bladder. Whenever possible, the same study staff member should perform the measurement for a given patient to minimize variability.
8. For patients ≥18 years of age, height needs to be measured at Screening only. Height (cm) will be measured, without shoes, socks, or hats, using a wall-mounted stadiometer. All measurements will be done in triplicate at each time point and recorded to the nearest half cm.
9. Body composition assessment will be performed using DXA. If DXA is not available at the clinic, this procedure may be skipped, with prior approval of the Sponsor.
10. All blood pressure (BP) and heart rate (HR) measurements are to be obtained with the patient in the sitting position following at least 5 minutes of rest. All measurements will be taken in triplicate, approximately 2 minutes apart. When possible, BP should be taken in the non-dominant arm throughout the study, using the same methodology (automated or manual). Body temperature (°C) and respiration rate (breaths/minute) will be obtained in the sitting position following at least 5 minutes of rest.
11. A single 12-lead ECG will be performed in the supine position following a period of at least 10 minutes of rest. At V2, the ECG will be performed before and 4 hours after dosing, and at V3 and V6, the ECG is to be performed at 4 hours after dosing.
12. A urine pregnancy test may be performed to expedite availability of results prior to dosing on Day 1. All other pregnancy tests will be serum tests; dosing may continue with results pending.
13. Collected prior to study drug administration.
14. Daily hunger questionnaire scores will be recorded prior to the patient's morning meal. During Screening, the patient must complete the daily hunger questionnaire in the electronic diary at least 4 of the 7 days prior to V2, paper version can be used if required. Patients who do not meet this requirement should not be enrolled into the study. V2 may be rescheduled if needed to fulfill this requirement with Sponsor approval.
15. In order to be eligible for the study, an individual patient's PHQ-A or PHQ-9 score must be <15 at Screening. If at any time during the study an individual patient's PHQ-A or PHQ-9 score is ≥10, the patient should be referred to a Mental Health Professional (MHP).
16. The PHQ-A will be administered to patients 11-17 years old and the PHQ-9 will be administered to patients ≥18.
17. In order to be eligible for the study, a patient at Screening cannot have a suicidal ideation of type 4 or 5, any lifetime history of a suicide attempt, or any suicidal behavior in the last month. If at any time during the study a patient has a suicidal ideation of type 4 or 5, or any suicidal behavior, the patient should be referred to an MHP.
18. The SF-12 will be administered to patients ≥18 years of age and the SF-10 will be administered to the parents/caregivers of patients <18 years of age.

[figure not shown]
20. IWQOL-Lite-CT will be administered to patients  $\geq 18$  years of age.
21. The EQ-5D-5L will be administered to patients  $\geq 16$  years of age. The EQ-5D-Y will be administered to patients  $> 8$  up to  $< 16$  years of age. In patients under the age of 8 years of age will not complete the EQ-measures.
22. Safety laboratory tests will include: complete blood count with differential (platelet count, red blood cell [RBC] count, hemoglobin, hematocrit, neutrophils, lymphocytes, monocytes, eosinophils, basophils) and standard indices (mean corpuscular volume, mean corpuscular hemoglobin, %reticulocytes), chemistry panel (includes sodium, potassium, chloride,  $\text{CO}_2$ , albumin, total protein, glucose, BUN, creatinine, uric acid, AST, ALT, GGT, CPK, alkaline phosphatase, total bilirubin, direct bilirubin, LDH, calcium, phosphorus), and urinalysis with microscopic analysis if positive findings on dipsticks warrant further examination.
23. Blood samples will be collected prior to dose administration in the fasting state for total cholesterol, high-density lipoprotein cholesterol, low-density lipoprotein cholesterol, and triglycerides.
24. Injection site evaluations and scoring (by the clinical staff) will include identification and measurement of areas of erythema, edema, and induration, as well as the presence of localized pain, tenderness, and itching. Additional evaluation data can be collected at any visit in which there are injection site reactions, even if not a time point for formal assessment.
25. Site personnel will call the patient on Day 15 to confirm the proper dose escalation has occurred and to collect AEs.
26. All patients must have evidence of hypothalamic injury on MRI completed within 8 months of Screening. If no MRI is available, then it may be repeated during the Screening Period.
27. Patients/caretakers will draw up and self-administer/administer the drug once daily in the morning beginning the morning of Day 1 and for the duration of dosing. On days with clinic visits, the patients/caretakers will administer the drug in the clinic in the presence of the clinical staff to assure proper technique.
28. Patients/caretakers will return all (the number recorded) used vials to the clinic when they visit, and both clinic-administered study drug as well as outpatient study drug administration will be recorded in a study diary.
29. AEs will be recorded from the time a patient provides informed consent. AEs reported after dosing on Day 1 will be considered TEAEs.

[figure not shown]
\* FSH should be measured in women who have been post-menopausal  $> 12$  months and should be in post-menopausal range.

[figure not shown]
## 16.2 Changes in Analysis Planned in the Protocol

**Table 5 Changes in Analysis Planned in the Protocol**

CSP Section	SAP section	Description/Rationale of Change

## 16.5 Multiple Imputation Methods

As stated in [Section 11.1](#), the MI procedure may be performed as needed as a sensitivity analysis. If performed, the following methods will be used:

Missing data for Week 16 will be imputed using MI under the Missing at Random (MAR) assumption. Change from baseline in BMI will be derived from the corresponding imputed values. The following steps will be followed to create the imputations:

- 1.1. Regardless of the actual pattern of missing data, the Markov Chain Monte Carlo (MCMC) method of the SAS PROC MI procedure will first be used to make it monotone. The single chain method will be used. The minimum values for imputed variables will be set to 0, in order to force PROC MI to redraw another value for imputation when an intended imputed value is less than the 0. Imputed values will be rounded to the nearest integer. The seed number will be set to 112595 and 5 imputations will be created.
- 1.2. The SAS PROC MI will be used for imputing missing values of data with monotone missing pattern. One imputation will be made using each of the 5 MCMC-imputed datasets. A linear regression model will be used with covariates for non-missing BMI from earlier scheduled time points including baseline as well as age. The minimum values for imputed variables will be set to 0, in order to force PROC MI to redraw another value for imputation when an intended imputed value is less than the 0. Imputed values will be rounded to the nearest integer. Change from baseline in BMI will be derived from the corresponding imputed values.
- 1.3. If the monotone pattern does not converge, the imputations will be created with an arbitrary missing data pattern. The seed number will still be set to 112595 and 5 imputed datasets will be created by fully conditional specification (FCS). One imputation will be made using each of the 5 imputed datasets. A linear regression model will be used with covariates for non-missing data from earlier scheduled time points including baseline as well as age. The minimum values for imputed variables will be set to 0, in order to force PROC MI to redraw another value for imputation when an intended imputed value is less than the 0. Imputed values will be rounded to the nearest integer. Change from baseline will be derived from the corresponding imputed values.
2. The imputed datasets will be analyzed as specified in the respective Section 9.
3. The resulting analysis on the imputed datasets will then be combined to produce a single set of statistics as follows.
  - 3.1. For any binary outcome, the results from the exact binomial test will be combined to produce a pooled proportion, 95% CI, and p-value using the SAS PROC MIANALYZE procedure.
  - 3.2. For any continuous outcome, the results from the ANCOVA analysis will be combined using SAS PROC MIANALYZE.

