6.1. Inclusion Criteria

Patients must meet all of the following criteria to be eligible for study participation:

1. Patient has documented evidence of HO, including:
 - a. Recent (within the previous 8 months before Screening) evidence of hypothalamic injury on magnetic resonance imaging (MRI); AND
 - b. Diagnosis of craniopharyngioma or other non-malignant brain tumor affecting the hypothalamic region; AND
 - c. Has undergone surgery, or chemotherapy, or radiation ≥ 6 months and ≤ 15 years before Screening.
2. Patient has either unilateral hypothalamic lesions (at least 6 patients) or bilateral hypothalamic lesions (at least 7 patients), as assessed by MRI.

Note: Although the intention of the study is to enroll at least 6 patients with unilateral hypothalamic lesions, the Sponsor may decrease the required number during the course of the study.
3. Aged 6 to 40 years, inclusive, at time of enrollment. (A maximum of 10 patients between the ages of 6 and 12 will be enrolled in the study.)

4. Obesity, documented by a BMI $\geq 35 \text{ kg/m}^2$ for patients ≥ 18 years of age or BMI $\geq 95^{\text{th}}$ percentile for age and gender for patients 6 to <18 years of age based on the US Centers for Disease Control and Prevention criteria.
5. Documented increase in BMI (change from pre-surgery baseline in BMI Z-score ≥ 0.2 for patients <18 years of age or BMI $>5\%$ for patients ≥ 18 years of age) either during the first 6 months following surgery or within 1 year before surgery AND still present at Screening.
6. More than 6 months after the end of post-tumor treatment, including chemotherapy, surgery, or radiation.
7. Patient must meet one of the following contraception requirements:
 - If a female of childbearing potential, defined as fertile, following menarche and until becoming post-menopausal unless permanently sterile (hysterectomy, bilateral salpingectomy, or bilateral oophorectomy), must use a highly effective form of contraception as outlined in Section 9.19.5.
 - If a female of non-childbearing potential, defined as permanently sterile (status post hysterectomy, bilateral oophorectomy, or bilateral salpingectomy) or post-menopausal for at least 12 months (and confirmed with a screening follicle-stimulating hormone [FSH] level in the post-menopausal laboratory range), contraception is not required during the study.

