## 4 General Analysis Conventions

All tables, listings, and figures will be programmed using SAS Version 9.4 or higher. Data collected in this study will be documented using summary tables and patient data listings created by using the SAS® system. Confidence intervals (CI) will be performed at a significance level of 5%, unless otherwise specified. Data for all patients in the clinical database will be included in the data listings. Calculated (derived) variables will be listed as appropriate.

All efficacy, safety and baseline characteristics variables will be presented using descriptive statistics and figures as appropriate. Continuous variables will be summarized using descriptive statistics (number of observations, mean, standard deviation (SD), median, minimum, and maximum). Categorical variables will be presented in frequency tables with number and percent of observations for each level. Missing counts for all variables will be presented for informational purposes only and will not be included in percentage calculations.

Study days will be calculated relative to the first injection of study drug. Day 1 will be the first day of study drug administration in the study. In data listings, the relative study day (in relation to date of first study drug administration) of all dates will be presented.

Adverse events, medical history events, and concomitant treatments/procedures will be coded using Medical Dictionary for Regulatory Activities (MedDRA), Version 24.0 or higher. Prior/concomitant medications will be coded using the World Health Organization (WHO) Drug Dictionary Global B3, March 2021 or higher.

Any changes from the SAP will be detailed in the Clinical Study Report (CSR).

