## 9.1 Primary Efficacy Endpoint

The primary endpoint is defined as the proportion of patients who achieve at least 5% BMI reduction from baseline, at ~16 weeks of treatment with setmelanotide. BMI will be calculated using patient's weight and height assessments, using the following formula:

$$BMI = \frac{kg}{m^2}$$

If needed, weight and height will first be converted into kilograms and meters, respectively. Given that body weight is collected in triplicates at each visit, weight (kg) will first be aggregated into one averaged weight per visit. Visits will then be compared against the analysis visit window (described in [Section 4.2](#)) to select the Week 16 averaged weight prior to calculating BMI and change in BMI. Patients who are  $\geq 18$  years of age will only have height measurement done at screening; the averaged triplicate

screening height will be used for the height component of the BMI calculation at each visit. Patients who are < 18 years of age will have their height measured in triplicates at most study visits. As with body weight, height will first be aggregated into one averaged height per visit and compared against the analysis visit window to select the Week 16 averaged height. Regardless of reason, if height is missing for an analysis visit, then height will be imputed using last observation carried forward (LOCF). Change ( $\Delta$ ) in BMI (%) from baseline at 16 weeks of treatment will be calculated as follows:

$$\Delta \text{ BMI } (\%) = \left( \frac{\text{Week 16 BMI} - \text{Baseline BMI}}{\text{Baseline BMI}} \right) * 100$$

An indicator variable will then be created to identify patients that have a decrease in BMI from baseline to Week 16 of 5% or more, allowing for the analysis of proportion of patients who achieve at least 5% BMI reduction.

The primary endpoint will be assessed using an exact binomial test at a 1-sided 0.05 significant level, compared to the null hypothesis proportion of 0.05 (which comes from a historical control rate of 5%). The number of and the binomial proportion of patients who achieve at least 5% BMI reduction from baseline at 16 weeks, the corresponding 2-sided 90% CI, and one-sided binomial test p-value will be presented. The Clopper-Pearson method will be used to calculate the CI. A scatter plot figure will also be created plotting each patient's percent BMI reduction from baseline to Week 16.

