### **11 Statistical/Analytical Issues**

#### **11.1 Handling of Missing Data**

In general, the number of patients with missing values will be summarized and reported as appropriate in all outputs. Calculations for all questionnaires will follow the methods specified in the specific sections of this SAP for the handling of the data.

For primary and key secondary analyses, missing data for Week 16 body weight and BMI will be imputed using LOCF. With the LOCF imputation method, if a patient is missing their Week 16 assessment, their last non-missing assessment will be used. Given that BMI will be calculated using patient's weight and height measurements, if height is missing for any analysis visit, height will be imputed using LOCF.

The primary analysis may be repeated using multiple imputation (MI) as a sensitivity analysis as needed. If performed, MI methods are specified in [Section 16.5](#).

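### The optional multiple-imputation analysis rounds imputed BMI to whole kg/m², which shifts the 5% responder cut for most imputed patients, and its pooling step uses a 95% CI with no stated standard error

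*SAP*

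**What the plan says.** SAP 11.1 makes the analysis discretionary: "The primary analysis may be repeated using multiple imputation (MI) as a sensitivity analysis as needed". If it is done, SAP 16.5 fixes the method.

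- **Imputation (steps 1.1–1.3).** Five datasets are created. Step 1.2 regresses BMI on earlier BMI values and age. Each of the three steps states "Imputed values will be rounded to the nearest integer", and the change from baseline is derived from the rounded values.
- **Analysis (step 2).** "The imputed datasets will be analyzed as specified in the respective Section 9". For the primary endpoint this is SAP 9.1: a responder has "a decrease in BMI from baseline to Week 16 of 5% or more", tested by a one-sided exact binomial test against 0.05, with "the corresponding 2-sided 90% CI, and one-sided binomial test p-value will be presented". The interval is Clopper-Pearson. Observed BMI comes from averaged weight and height, and no rounding is stated.
- **Pooling (step 3.1).** For any binary outcome, "the results from the exact binomial test will be combined to produce a pooled proportion, 95% CI, and p-value", using PROC MIANALYZE. No standard error or transformation is named.

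The 95% level matches the default in SAP 4 ("Confidence intervals (CI) will be performed at a significance level of 5%, unless otherwise specified"), but SAP 9.1 does specify otherwise for this endpoint.

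**The concern.** A sensitivity analysis for missing data should change the missing-data assumption and nothing else. This one changes three further things.

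1. Rounding can move an imputed BMI by up to 0.5 kg/m². That is 1.4% of a BMI of 35 and 2.5% of a BMI of 20, against a cut of 5%. Observed patients are not treated this way.
2. The CI level goes from 90%, which matches the one-sided 0.05 test, to 95%.
3. Rubin's rules need an estimate and a standard error from each dataset. An exact test and a Clopper-Pearson interval supply no standard error, so the programmer must choose one. The trial is open-label, so that choice could be made with results in view.

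If the pooled result differed from the primary, a reader could not tell whether missing data or one of these choices was the cause.

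**Working it through.** The plan gives no numerical figure for this analysis, so there is none to reproduce.

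**Inputs from the documents:** 5% responder cut, null 0.05, one-sided 0.05, 90% CI (SAP 9.1); 5 imputations, integer rounding, 95% CI (SAP 16.5); about 15 patients, up to 10 of them aged 6 to 12 (SAP 3.2.1); adult entry BMI of at least 35, with a percentile criterion and no kg/m² floor for children (Protocol 6.1).

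**Assumptions:** 2 of 15 missing at Week 16; paediatric BMI 20–35; percent change in BMI normal with mean −3, −5 or −10 and SD 4, 5 or 7 points; the responder counts below.

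**Effective cut.** With baseline B, an imputed patient is a responder if the rounded BMI is at most 0.95B, that is, if the unrounded draw is below floor(0.95B) + 0.5. So

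cut = 1 − (floor(0.95B) + 0.5)/B

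| B | floor(0.95B) | Effective cut |
|---|---|---|
| 20 | 19 | 1 − 19.5/20 = 2.50% |
| 30 | 28 | 1 − 28.5/30 = 5.00% |
| 35 | 33 | 1 − 33.5/35 = 4.29% |
| 40 | 38 | 1 − 38.5/40 = 3.75% |
| 42 | 39 | 1 − 39.5/42 = 5.95% |
| 50 | 47 | 1 − 47.5/50 = 5.00% |

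On a continuous scale the cut runs from 3.60% to 6.40% for B = 35–45, with both extremes on either side of B ≈ 35.79, and from 2.5% to 7.4% for B = 20–35. The mean cut over 35–45 is 5.00%. For one patient the cut is the same in all five datasets, so more imputations would not remove the shift.

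**Effect on one patient.** Shift in responder probability = Φ((−cut − mean)/SD) − Φ((−5 − mean)/SD), with the cut in percent. Over B = 35–45 and the nine scenarios, the largest shift is about 13.7 points in either direction (mean −5, SD 4, B ≈ 35.79). Averaged over 35–45 it is within 0.4 points of zero in every scenario.

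**Effect on the pooled proportion.** Two imputed patients, both near the worst adult baseline: 13.7 × 2/15 = 1.8 points. One patient is 1/15 = 6.7 points.

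**Pooling.** Let q be the mean proportion, W the mean within-dataset variance, V the between-dataset variance. T = W + 1.2V, df = 4(1 + W/(1.2V))², t = (q − 0.05)/√T.

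Counts 3,3,3,4,4 of 15: q = 17/75 = 0.227, V = 0.00133. The five exact p-values are 0.036 (3/15) or 0.0055 (4/15), so all reject.

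| Standard error | W | √T | t (df) | One-sided p |
|---|---|---|---|---|
| Wald, p(1−p)/n | 0.01161 | 0.115 | 1.54 (273) | 0.063 |
| Null-based, 0.05 × 0.95/15 | 0.00317 | 0.069 | 2.56 (35.5) | 0.007 |

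**CI level.** Counts 4,4,4,5,5, Wald: q = 0.293, √T = 0.124, lower limit 8.9% at 90% and 4.97% at 95%. With no between-dataset variance, 3/15 gives Clopper-Pearson lower limits of 5.7% (90%) and 4.3% (95%). In both cases the level alone moves the limit across the 5% null.

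**How often this could matter.** With 13 observed, 2 imputed and Wald pooling, enumerating every pattern of imputed responders found neither disagreement (five exact rejections with pooled p above 0.05; 90% limit excluding 5% while the 95% limit does not) at 5 or 6 observed responders. Some patterns at 2, 3 or 4 did show one. At the planned 40% rate, P(5 or more of 13) = 65% and P(2 to 4) = 34%.

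**The case against.** The strongest reply is that little depends on this. Multiple imputation is run only if wanted, SAP 9.1.1 lists only the per-protocol repeat as a sensitivity analysis, and if no Week 16 value is missing nothing changes. That stands, and it sets the priority.

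A reader might infer that rounding biases the responder rate in one direction, or moves the cut for every imputed patient. Neither holds. The cut stays at exactly 5% at baselines such as 30 or 50, and the shifts average about zero across baselines. What remains is that a handful of imputed patients need not average out. Nor is the adult range a bound for this trial, since up to 10 patients may be aged 6 to 12 and shifts in the cut are larger at lower BMI.

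A reader might also infer that the null and the side of the test are missing altogether. Step 2 points to SAP 9.1, which supplies both for each dataset, and a one-sided test against 0.05 is the natural reading at pooling. Likewise the 95% level is openly stated and follows the general default. It is a mismatch to tidy, not a hidden change. The standard error is the real gap.

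Finally, naming a standard error does not by itself cure the p = 0.063 example. If Wald is named, the pooled p and its 90% lower limit of 3.7% still disagree with five exact rejections. That is correct, and the fix allows for it.

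**Conclusion.** The concern holds, at low priority. The integer rounding is wrong as written: it gives most imputed patients an effective cut other than 5%, from 3.6% to 6.4% for baselines 35–45, and the SAP gives no reason for it. Its effect on the pooled proportion is small, about 1.8 points in an adverse adult case with 2 of 15 missing. The pooling step matters more near the critical count of 3 of 15, where the unstated standard error or the CI level can decide the result. These sizes rest on the assumed missing number, responder counts, change distribution and paediatric BMI range.

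The documents do not support reading this as a threat to the primary result. The exact test and the LOCF analysis use neither the rounding nor the pooling step.

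**What to change.** In SAP 16.5:

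- **Steps 1.1–1.3:** delete the integer rounding and derive the responder flag from unrounded imputed BMI.
- **Step 3.1, for the primary endpoint:** use a 90% CI and a one-sided test against 0.05; name in advance the standard error or transformation used for pooling; label the pooled result approximate; and report the five per-dataset exact p-values beside it, so that a disagreement caused by the approximation is visible.

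The cost is three deleted sentences, one reworded step and a few program lines. Data collection and the primary and LOCF analyses do not change.
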